**Statement of Compliance**

The trial will be conducted in accordance with International Conference on Harmonisation Good Clinical Practice (ICH GCP), applicable United States (US) Code of Federal Regulations (CFR), and the WCMC Institutional Review Board (IRB) Terms and Conditions of Award. The Principal Investigator will assure that no deviation from, or changes to the protocol will take place without prior agreement from the Investigational New Drug (IND) or Investigational Device Exemption (IDE) sponsor, funding agency and documented approval from the Institutional Review Board (IRB), except where necessary to eliminate an immediate hazard(s) to the trial participants. All personnel involved in the conduct of this study have completed Human Subjects Protection and ICH GCP Training.

The protocol, informed consent form(s), recruitment materials, and all participant materials will be submitted to the IRB for review and approval. Approval of both the protocol and the consent form must be obtained before any participant is enrolled. Any amendment to the protocol will require review and approval by the IRB before the changes are implemented to the study. All changes to the consent form will be IRB approved; a determination will be made regarding whether a new consent needs to be obtained from participants who provided consent, using a previously approved consent form.

**List of Abbreviations**

AE	Adverse Event
CFR	Code of Federal Regulations
CRF	Case Report Form
CTSC	Clinical Translational Science Center
DSMB	Data Safety Monitoring Board
DSMP	Data Safety Monitoring Plan
FDA	Food and Drug Administration
GCP	Good Clinical Practice
HIPAA	Health Insurance Portability and Accountability Act of 1996
HRBFA	Human Research Billing Analysis Form
HUD	Humanitarian Use Device
ICF	Informed Consent Form
IDE	Investigational Device Exemption
IND	Investigational New Drug
IRB	Institutional Review Board
NRS-11	Numerical Pain Score
PHI	Protected Health Information
PI	Principal Investigator
REDCap	Research Electronic Data Capture
SAE	Serious Adverse Event
SUSAR	Suspected Unexpected Serious Adverse Reaction
UIRTSO	Unanticipated Problem Involving Risks to Subjects or Others
WCM	Weill Cornell Medicine

## 1. Protocol Summary

Full Title:	Multi-modal Analgesia to Reduce Narcotics After Scrotal Surgery
Short Title:	Narcotic Reduction After Surgery
Clinical Phase:	III
Principal Investigator:	[name]
Study Description:	The use of non-narcotic multi-modal analgesia to be used in the pre-operative, peri-operative and post-operative period to reduce or potentially eliminate narcotic usage following scrotal surgery. We have shown that the use of anti-inflammatories in the peri-operative period reduce both pain and narcotic use. Our hypothesis is that adding another agent in the multi modal pathway will further reduce pain and potentially reduce narcotic usage.
Sample Size:	N= 86 (43 participants in each arm)
Enrollment:	This study will enroll 86 participants but will screen 114 participants accounting for an approximate 25% screening failure rate.
Study Population:	Participants undergoing microsurgical testicular sperm extraction for non-obstructive azoospermia.
Enrollment Period:	2 years.
Study Design:	Double-blind, placebo-controlled, randomized trial Two study arms (43 participants per arm) Addition of gabapentin pre- and post-operatively
Description of Sites/	
Facilities Enrolling	
Participants:	This will be a single center study at Weill Cornell Medicine/New York Presbyterian Hospital.
Study Duration:	December 31, 2023
Participant Duration:	7 days.
Study Agent/Device Name	
Intervention Description:	Arm #1 – Gabapentin 600mg taken pre-operatively and 300mg taken three times a day for 3 days. Arm #2 – Placebo taken pre-operatively and three times a day for 3 days.
Primary Objective:	Pain scores
Secondary Objectives:	Narcotic consumption
Exploratory Objectives:	Symptom modification (ie. nausea)
Endpoints:	Numerical pain rating scale Narcotic prescription usage

### 1.1 Schema

## 1.2 Study Objectives

### 1.2.1 Primary Objectives

To compare participant reported pain between participants receiving gabapentin and those receiving placebo in addition to standard of care. This will be assessed using the 11-point numerical pain rating scales (NRS-11) from post-operative day 1 to 7.

### 1.2.2 Secondary Objectives

To assess narcotic use following surgery including the number of tablets taken, frequency and time when narcotic is initially utilized. Study participants satisfaction will be documented.

## 2. Background

### 2.1 Disease

Microdissection testicular sperm extraction (microTESE) is the gold standard for sperm retrieval in research study participants with non-obstructive azoospermia for in vitro fertilization. Scrotal and testicular surgery can be associated with post-operative pain and improper narcotic utilization has become a significant societal problem.

### 2.2 Investigational Agent/Device, or Research intervention

Multi-modal analgesia has been used as an alternative to reduce narcotic usage in the peri-operative and post-operative period following scrotal surgery. Our previous work has looked at the role of anti-inflammatories, specifically COX-2 inhibitors, for this purpose and has shown a reduction in both post-operative pain and narcotic usage. The addition of other non-narcotic analgesics may reduce and potentially eliminate narcotic usage following scrotal surgery.

Gabapentin is a well-known anti-convulsant medication that is commonly used by pain specialists in their approach to multi-modal pain control. It is most often used to treat neuropathic pain often characterized by a burning or itching cessation and may be related to diseases such as diabetes.

Gabapentin is a ligand of the a2delta subunit of voltage gated calcium channels, but the mechanism of action by which gabapentin facilitates pain reduction is unclear, various hypotheses exist including reduced hyperexcitability of neurons resulting in central desensitization, decreased calcium entry caused by binding to the dorsal horn neurons reducing neurotransmitter release or through other channels such as sodium or NMDA channels. Gabapentin is water soluble and rapidly absorbed with dose-dependent bioavailability, with a half-life of approximately 5-7 hours. For this reason it is commonly dosed up to three times per day. It is cleared renally, and not metabolized and has no

impact on hepatic enzymes. The medication is generally well tolerated with the most common effects of somnolence and dizziness, and does not need to be taken with meals.

Previous studies have examined the role of gabapentin for relief of acute pain in the peri-operative period. Studies in the plastic surgery literature, obstetrical literature, general surgery literature and orthopedic literature have examined its use with varying impacts. Various doses and schematics for administration have been studied, including meta-analyses, which show conflicting results. Doses have been reported from 300mg-1200mg in these studies, and given before surgery and for a short duration afterwards. Some studies have also studied the combination of celecoxib with gabapentin showing an improved benefit in both pain scores, as well as side effect reduction. A lack of robust, large and well controlled trials have been completed.

Overall gabapentin has been shown to have minimal drug interactions due to its pharmacokinetics. Studies that have been completed often show varied results.

Gabapentin is a FDA approved medication prescribed for the treatment of partial or focal seizures in adults and children, and for the management of post-herpetic neuralgia. The use of gabapentin in this study is considered investigational (ie. it is used for an unapproved indication). Investigators seek an IND exemption as the study uses gabapentin to assess pain reduction and gabapentin consumption after scrotal surgery. This study does NOT intend to support a significant change in the advertising for a prescription product, FDA approval of a new indication or a significant change in the product labeling, or FDA approval of change in route of administration, dose, and/or patient population.

## 2.3 Rationale

Pain management is an ongoing issue for all surgeons, and with rising concerns regarding opioid addiction and consumption, multi-modal strategies and alternatives are necessary. Given that we have previously shown the role of anti-inflammatory medications reducing narcotic usage in the peri-operative period in addition to acetaminophen, we believe addition of another agent may reduce narcotic use completely. No literature to our knowledge is available regarding the use of gabapentin in urologic surgery, and given its potential benefit in other surgeries we believe this will further reduce pain and possibly eliminate narcotic usage post scrotal surgery.

## 2.4 Risk/Benefit Assessment

### 2.4.1 Known Potential Risks

As per the FDA, gabapentin side effects commonly include dizziness and drowsiness. Other reported adverse events include headache, lack of coordination, viral infection, nausea and vomiting, difficulty speaking, tremor, swelling, fever, jerky movements, difficulty with coordination, double vision and unusual eye movement.

#### **2.4.2 Known Potential Benefits**

The benefits of the medication include known research showing improved pain control in certain populations. This could potentially reduce narcotic consumption and reduce costs associated with narcotic dependence and addiction.

#### **2.4.3 Assessment of Potential Risks and Benefits**

The research intervention has numerous health benefits to the individuals who will be participating in the study. Improved health outcomes are expected due to the research intervention such as better pain control in scrotal and urologic surgery, and clinical practice pertaining to reduced prescription and consumption of narcotics amongst patients with non-obstructive azoospermia undergoing scrotal surgery.

### **2.5 Correlative Studies Background**

Not applicable

## **3. Study Design**

### **3.1 Overall Design**

This will be assessed in a phase III randomized, double-blind control trial. All eligible subjects will be included and enrolled sequentially from the study start date. The study will include two arms ( gabapentin or placebo) at a single site in patients undergoing microsurgical testicular sperm extraction.

### **3.2 Scientific Rationale for Study Design**

This study will use two arms to study the efficacy of gabapentin. A placebo will be used in order to blind the participants to reduce bias. The study will be designed to test superiority compared to placebo. The potential problems relate to the side effects of the medications themselves, otherwise all participants will receive sufficient analgesia in order to control their post-operative pain.

### **3.3 Justification for Dose**

The dose for gabapentin will be in keeping with data from the literature and routine clinical practice. Various studies have examined doses from 300mg-1200mg, and while some have shown increased effects at maximal doses this is also associated with more side effects. Given the outpatient nature of this procedure and many scrotal surgeries, dosing on the lower end was more justified with 600mg given 2 hours before surgery, and 300mg three times a day for 3 days.

### **3.4 End of Study Definition**

A participant is considered to have completed the study if he or she has completed all phases of the study including the last pain score assessment and record of narcotic consumption on post-

operative day #7 as shown in the Schedule of Assessments (SoA), Section 6.1. The end of the study is defined as return of the pain score and narcotic consumption at post-operative follow-up visit.

#### **4. Subject Selection**

##### **4.1 Study Population**

Subjects undergoing microsurgical sperm extraction who meet the inclusion and exclusion criteria will be offered participation in this study.

##### **4.2 Inclusion Criteria**

1. Participants undergoing microsurgical testicular sperm extraction
2. Participants over 18 years of age who can provide informed consent
3. Participants with no contraindication to the consumption gabapentin or documented allergy/intolerance
4. Participants not currently using opiates for another reason

##### **4.3 Exclusion Criteria**

1. Contraindication to the consumption of celecoxib or gabapentin
2. History of substance abuse (including prior opiate abuse)
3. Narcotic use within last 3 months
4. Any of the following comorbidities: renal failure, heart disease, peptic ulcer disease, cerebrovascular disease, significant liver disease, untreated depression, chronic pain disorder, or bleeding diatheses
5. Medical history or concurrent illness that the investigator considers sufficiently serious to interfere with the conduct, completion, or results of this trial, or constitutes an unacceptable risk to the subject

##### **4.4 Lifestyle Considerations**

Not applicable.

##### **4.5 Screen Failures**

Screen failures are defined as participants who consent to participate in the clinical trial but are not subsequently randomly assigned to the study intervention or entered in the study. A minimal set of screen failure information is required to ensure transparent reporting of screen failure participants, to meet the Consolidated Standards of Reporting Trials (CONSORT) publishing requirements and to respond to queries from regulatory authorities. Minimal information includes demography, screen failure details, eligibility criteria, and any serious adverse event (SAE).

Individuals who do not meet the criteria for participation in this trial (screen failure) because of an inability to take either study drug may be rescreened. Rescreened participants should be assigned the same participant number as for the initial screening.

#### 4.6 Strategies for Recruitment and Retention

Participants will be recruited sequentially as any patient undergoing microsurgical testicular sperm extraction at Weill Cornell/New York Presbyterian Hospital by [name]. All participants over 18 years of age will be considered.

We anticipate an accrual rate of 80% from a single site. These study participants will be recruited in the clinic at the time of surgical consent.

Participants will be identified and approached by a member of the research team.

Participants will not receive any compensation for their participation in the study.

### 5. Registration Procedures

#### 5.1 Subject Registration (WCM only)

Subjects will be registered within the WRG-CT as per the standard operating procedure for Subject Registration.

### 6. Study Procedures

#### 6.1 Schedule of Assessments

**Table 1. Schedule of trial events**

	Pre-Study	Day of Surgery	POD #1	POD #2	POD #3	POD #7	Off Study
Agent Administration		X	X	X	X		
Informed consent	X						
Demographics	X						
Medical history	X						
Concurrent meds	X						
Outcome Evaluation (Pain Scores)		X	X	X	X	X	
Outcome Evaluation (Narcotic Usage)		X	X	X	X	X	

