### **6.1.1 Screening Visit (-7 days before start of Research Intervention)**

- Informed consent
- Medical history
- Medication history

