## **12.2 Statistical Analysis**

The primary objective of this double-blind, placebo controlled randomized trial is to compare the participant-reported pain scores taken on an 11-point numerical rating scale (NRS-11) between subjects who received Gabapentin and controls who received placebo on day-7 post-scrotal surgery. The secondary objective is to determine whether the addition of gabapentin for post-operative pain control reduces narcotic intake. This study will also explore the effect gabapentin has on symptom modification.

Assuming a baseline NRS-11 score of 3.8 (from previous study) and a goal is to detect a two-point difference (reduction) in the day-7 pain score between the two groups, a sample size of 86 participants (43 per arm) will yield a power of 80% when using a two-sample t-test with a 0.05 two-

sided significance level. To account for potential loss to follow up and drop-out at a rate of 25%, each arm will require 43 study participants for a total recruitment of 86 study participants. This calculation assumes a standard deviation of 2.9, which is based on a previous study that looked at the effect of celecoxib in the same patient setting.

Approximately 150 to 250 microTESE procedures are conducted at our site annually. As a result, we plan to accrue and complete the study in 29 months (i.e. ~9 study participants per month).

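### The plan defines no pre-treatment NRS-11 score, so it cannot be relied on to report starting pain by arm or to gain the modest precision of adjusting for it

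*Combined protocol and SAP*

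**What the plan says.** **Schedule.** Table 1 in section 6.1 has a row "Outcome Evaluation (Pain Scores)". It is marked on the day of surgery and on post-operative days 1, 2, 3 and 7, and is blank at Pre-Study. Section 6.1.1, headed "Screening Visit (-7 days before start of Research Intervention)", lists three items: consent, medical history and, last, "Medication history". None is a pain score.

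**Timing on the day of surgery.** Sections 3.3 and 12.1 put the first dose 2 hours before the operation. Table 1 marks agent administration and the pain score in the same Day of Surgery column, without giving their order. Sections 11.1 and 12.1 set survey times from post-operative day 1 only.

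**Sample size.** Section 12.2 begins "Assuming a baseline NRS-11 score of 3.8 (from previous study)" and aims to "detect a two-point difference (reduction) in the day-7 pain score between the two groups". It adds: "This calculation assumes a standard deviation of 2.9".

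**Analysis.** Section 12.2 compares day-7 scores by a t-test or Wilcoxon test and models days 1 to 7 by GEE. Neither is described with a baseline covariate, and no change-from-baseline analysis is planned.

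**The concern.** A pre-treatment score on the same scale is the usual first candidate as a covariate for a later pain score. If it predicts day-7 pain, adjusting for it removes part of the between-man variation from the treatment comparison. It also lets the report show how the two arms started.

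As written, the plan does not secure such a score. The Day of Surgery mark could be met by a score taken before the capsule, between the capsule and the operation, or after the operation. Only the first is a pre-treatment value. A score taken after dosing may already reflect treatment and should not be used as a baseline covariate. A pre-dose score that is not taken cannot be recovered later.

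The use of the word baseline in section 12.2 adds to the uncertainty, because the text does not say what the 3.8 measures.

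**Working it through.** **1. Does the schedule define a pre-treatment score?**
- Pre-Study column of Table 1: no pain score.
- Screening list, section 6.1.1: no pain score.
- Day of Surgery column: a pain score is marked, with no time relative to the capsule.
- Survey times, sections 11.1 and 12.1: none for the day of surgery.
- Narcotic-usage row of Table 1: the same marks as the pain row. Since section 4.3 excludes narcotic use in the last 3 months, a pre-operative narcotic count would have little meaning. This suggests, but does not prove, that both rows were meant to start after surgery.
- Section 15: pain scores appear among the study data, not in the list of demographic and history items.

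So no defined pre-treatment score exists, although one mark could be made into one.

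**2. Reproduce the plan's sample size.** Inputs from section 12.2: difference 2, SD 2.9, two-sided alpha 0.05, power 80%, loss 25%.
- The exact two-sample t-test needs 33.99, so 34 evaluable per arm.
- Allowing for loss: 34 × 1.25 = 42.5, rounded up to 43, which is the plan's figure.
- After the plan's own 25% loss: 43 × 0.75 = 32.25, so about 32 evaluable per arm.

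The 3.8 enters none of these steps. Changing it leaves the sample size as it is.

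**3. What would adjustment add?** For a covariate with correlation ρ to the outcome:
- residual SD = 2.9 × √(1 − ρ²)
- 95% CI half-width ≈ 1.96 × residual SD × √(2/n)
- power from the noncentral t distribution for a difference of 2

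The documents do not give ρ, so a range is assumed.

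| Assumed ρ | Residual SD | Power, 34 per arm | Half-width, 34 per arm | Power, 32 per arm |
|---|---|---|---|---|
| 0 | 2.90 | 80.0% | 1.38 | 77.5% |
| 0.2 | 2.84 | 81.6% | 1.35 | 79.2% |
| 0.3 | 2.77 | 83.6% | 1.32 | 81.2% |
| 0.5 | 2.51 | 89.9% | 1.19 | 88.0% |

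Example: at ρ = 0.3, 2.9 × √0.91 = 2.766, and 1.96 × 2.766 × √(2/34) = 1.32.

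The degree of freedom spent on the covariate is negligible. At 34 per arm and ρ = 0.3, power is 83.58% with 66 degrees of freedom and 83.56% with 65.

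For ρ up to 0.3 the gain is at most 3.6 percentage points at 34 per arm (83.6 − 80.0) and 3.7 at 32 per arm (81.2 − 77.5). The half-width narrows by at most 0.06 NRS points (1.38 − 1.32). The ρ = 0.5 row shows the upper end of the assumed range; nothing in the documents supports a value that high.

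**The case against.** **The comparison does not need a baseline score.** This stands. Allocation is 1:1 by permuted blocks (section 7.11), and the test's error rate already covers chance imbalance. The planned SD of 2.9 already contains whatever variation comes from starting pain. Adjustment adds precision only.

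**There may be little starting pain to adjust for.** This largely stands. Section 4.3 excludes chronic pain disorder and narcotic use in the last 3 months, section 4.2 excludes current opiate use, and the pain under study follows the operation. If pre-operative scores sit near zero, ρ is low and the gain is close to nil.

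**The Day of Surgery mark may already be a pre-dose score.** This stands in part. A reader might infer from the blank Pre-Study cell that the trial cannot adjust for starting pain at all. The documents do not support that: the day of surgery includes a period before the capsule, and the mark could be fixed there. The survey attachment mentioned in sections 11.1 and 12.1 is not among the documents and may say more. What the documents do show is that the timing is undefined.

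**The 3.8 is not a promise of a measured baseline.** This stands. A reader might take "Assuming a baseline NRS-11 score of 3.8 (from previous study) and a goal is to detect a two-point difference (reduction)" to mean a change from each man's own starting score, or to show that men start with substantial pain. The text supports neither. The figure comes from an earlier study, and the reduction is a day-7 difference between groups.

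**The 77.5% at 32 per arm is a dropout matter.** Agreed. It comes from how the allowance for loss was calculated and adds no weight here. It is shown only because 32 is what the plan's own loss rate leaves.

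**Conclusion.** The point holds as a minor improvement. The plan defines no pre-treatment NRS-11 score, leaves the Day of Surgery score without a stated time or a matching survey, and plans only unadjusted analyses. The primary comparison remains valid, and the planned 80% power with 34 evaluable per arm does not depend on adjustment.

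The loss is the ability to report starting pain by arm, plus some precision. How much precision depends on a correlation that the documents do not give: for 0 to 0.3 it is between nothing and just under 4 points of power. The low end is plausible given who is excluded. The case for acting rests on the very low cost and on the fact that the score cannot be collected afterwards.

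**What to change.** 1. Take one NRS-11 item at the Pre-Study visit, or on the day of surgery before the first capsule. Mark that timing in Table 1 and add the item to the survey schedule in sections 11.1 and 12.1. If a later score on the day of surgery is also wanted, list it separately.
2. Report the pre-treatment score by arm.
3. In section 12.2, prespecify it as a covariate in the day-7 comparison (ANCOVA) and in the GEE, with the unadjusted result as a sensitivity analysis.
4. In section 12.2, say what the 3.8 measures. If it is a post-operative control-arm mean, replace the word baseline.

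The cost is one extra question at a contact that already takes place, one degree of freedom in the model and a few lines of text. The downside is that the item may yield little if nearly all men score close to zero before surgery.
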